Interventional Template Version: 12 February 2020

US	United States
UP	Unanticipated problem
VAS	Visual analog scale
WOMAC	Western Ontario and McMaster Universities Osteoarthritis index
WOMRS	Whole-Organ Magnetic Resonance Imaging Score

CONFIDENTIAL

Protocol Summary

[figure not shown]
Title	Genicular Artery Embolization for Treatment of Knee Osteoarthritis (OA)
Short Title	Geniculate Artery Embolization for Treatment of Knee Osteoarthritis
Brief Summary	Single-arm, single-center, no sham or placebo, prospective pilot trial designed to evaluate the feasibility and safety of transcatheter arterial embolization in patients with knee OA. Eligible participants will receive geniculate artery embolization using Embosphere™ Color-Advanced Microspheres. Patients will be followed up for a total of 12 months.
Objectives	Primary objective: to determine the effectiveness of genicular artery embolization in reducing knee pain at 3-months post intervention in patients with knee OA. This will be assessed by evaluating the clinical success rate defined as at least 50% reduction in Western Ontario and McMaster Universities Osteoarthritis index (WOMAC) pain score from pre-intervention baseline to follow-up visit at 3 months post-intervention without an increase in baseline incidence of pain medication use or intra-articular injection. The WOMAC Score will be calculated from the Knee injury and Osteoarthritis Outcome Score (KOOS) score. Secondary objectives: 
 - To evaluate the safety of genicular artery embolization - To determine whether transcatheter arterial embolization improves OA-related knee symptoms and quality of life.
Methodology	Prospective, single-arm, single-center, no sham or placebo, pilot study
Endpoint	Primary endpoint: WOMAC pain score at 3-months post intervention. Secondary endpoints: 
 - Rate, type, causality, and severity of adverse events - WOMAC pain score at 1-, 12-, and > 12-months post intervention - Pain visual analog scale (VAS) - WOMAC knee stiffness and physical function scores at 1, 3, 12 months
Study Duration	3 years
Participant Duration	Each individual subject will be enrolled for approximately 13 months to complete all study visits from the initial screening visit to last follow up at 12-months post intervention. Participants that completed the 12 months visit by August 31, 2024 will be invited to participate in longer follow up (18 months – 48 months follow-up).
Population	40 patients, age 30-80, any gender, with grade 2,3, or 4 (in select subjects with no bone deformity) knee OA on the most recent knee radiographs obtained within 6 months of intervention

CONFIDENTIAL

Study Sites	Single center: NYU Langone Health Hospitals
Number of participants	Data from 40 patients will be required The study would accrue 50 patients to account for an attrition rate of 20%
Description of Study Agent/Procedure	Embozene™ Color-Advanced Microspheres are spherical, tightly calibrated, biocompatible, non-resorbable, hydrogel microspheres coated with an inorganic perfluorinated polymer used for embolization.
Key Procedures	Transcatheter arterial embolization of one or more genicular artery(ies) using Embozene™ Color-Advanced Microspheres
Statistical Analysis	The primary objective is to assess the clinical success rate, which will be summarized in terms of the observed proportion of patients manifesting a positive response and a two-sided exact 95% confidence interval (CI) per the Blyth-Still-Casella method (reference). The treatment will be declared a success if the data support the conclusion that at least 75% of treated patients show a positive response.

Schematic of Study Design

Prior to Enrollment

[figure not shown]
Day 0

Day 1

[figure not shown]
Day 30

Day 90

Day 360

CONFIDENTIAL

This material is the property of the NYU School of Medicine and Langone Medical Center. Do not disclose or use except as authorized in writing by the study sponsor
Interventional Template Version: 12 February 2020

Schedule of Activities

Visit #	Visit 1*	Visit2*	Visit 3	Visit 4**	Visit 5*	Visit 6*	Visit 7*	Visit 8***
Visit Description	Screening	Baseline	Intervention	1-day follow-up	1-month follow-up	3-month follow-up	12-month follow-up	>12 months
Eligibility screen	X							
Informed consent	X							
Demographics		X						
Medical history		X						
Adverse Events				X	X	X	X	X
Physical exam		X		X	X	X	X	X
Medication History		X			X	X	X	X
Pain VAS**		X			X	X	X	X
KOOS score		X			X	X	X	X
EQ-5D-5L scale		X			X	X	X	X
Previous treatments		X			X	X	X	X
Venous blood draws		X##	X##		X	X	X	X
Urine samples		X			X	X	X	X
Knee MRI		X ¹				X ³		
Knee radiograph		X ²						
Genicular artery embolization			X					

1- If not previously available (i.e., recent knee MRI within 3 months of screening); if MRI cannot be obtained on the same day due to subject preference and/or MRI scheduling related reasons, MRI can be performed anytime between the baseline visit and intervention visit
 
2- If not previously available (i.e., recent knee radiograph within 6 months of screening). Can be performed on a separate day based on appointment availability or subject's preference.
 
3- Post-procedural MRI can be done on a separate day of visit 6 based on appointment availability and subject's preference as long as it's performed within the timeframe of 3month +/- 10 days.
 
* Visit 1 and 2 can be combined based on subject preference. In that case, procedures listed in visit 2 will be performed after signing informed consent on the same day.
 
** Visit 4 (1-day follow-up) dates range can be +3 days (phone call, telemedicine, or in-person IR clinic visit determined by subject's preference and need for physical examination)
 
*** Visit 8. Optional visit for participants who completed 12 month follow up by August 31, 2024 (by invitation, voluntary, and after obtaining informed consent for this visit). This visit can be performed at any time interval within 18 months – 48 months
								

CONFIDENTIAL

post procedure. This visit can be performed by sending the questionnaire by a safe email and participants can email it back to research coordinator or PI OR by a phone call performed by research coordinator,
	
# 1, 3, 12-month follow-up dates range can be +/- 10 days
	
## The pre-procedural blood work can be done on the day of the procedure prior to performing the procedure based on subject's preference.
	
--	--	--	--

1 Key Roles

- **Principal Investigator (PI):** Will be one of two interventional radiologists performing the procedure. Will be responsible for study integrity, data monitoring, data collection, statistical analysis, and manuscript writing.

[name]

Clinical Assistant Professor of Radiology
Director, Vascular and Interventional Radiology Research Program
Department of Radiology, NYU Langone Health
[name]
[contact]
Email: [contact]

- **Co-PI:** Co-investigator involved in recruiting patients and conducting the clinical assessment for knee osteoarthritis

[name]

Associate Professor
Department of Internal Medicine, NYU Langone Orthopedic Center
[name]

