- **Severe AE:** marked escalation of care, ie, hospital admission or prolongation of existing hospital admission for > 24 hours, hospital admission that is atypical for the procedure, inpatient transfer from regular floor/telemetry to intensive care unit, or complex intervention performed requiring general anesthesia in previously non-intubated patient (generally excludes pediatrics or in circumstances in which general anesthesia would primarily be used in lieu of conscious sedation, eg, in mentally challenged or severely uncooperative patients);
- **Life-threatening or disabling event:** eg, cardiopulmonary arrest, shock, organ failure, unanticipated dialysis, paralysis, loss of limb or organ;
- **Patient death or unexpected pregnancy abortion.**

For AEs not included in the protocol defined grading system, the following guidelines will be used to describe severity.

- **Mild** – Events require minimal or no treatment and do not interfere with the participant's daily activities.
- **Moderate** – Events result in a low level of inconvenience or concern with the therapeutic measures. Moderate events may cause some interference with functioning.
- **Severe** – Events interrupt a participant's usual daily activity and may require systemic drug therapy or other treatment. Severe events are usually potentially life-threatening or incapacitating.

8.2.2 **Relationship to Study Device**

CONFIDENTIAL

For all collected AEs, the clinician who examines and evaluates the participant will determine the AE's causality based on temporal relationship and his/her clinical judgment. The degree of certainty about causality will be graded using the categories below according to the new adverse event classification by the Society of Interventional Radiology Standards of Practice Committee

- Category 1: AE not caused by procedure. The AE is completely independent of study drug administration, and/or evidence exists that the event is definitely related to another etiology. There must be an alternative, definitive etiology documented by the clinician.
- Category 2: Unknown whether AE was caused by the procedure.
- Category 3: AE caused by the procedure. There is clear evidence to suggest a causal relationship, and other possible contributing factors can be ruled out.

The definition implies a reasonable possibility of a causal relationship between the event and the study device. This means that there are facts (evidence) or arguments to suggest a causal relationship.

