8.2.3 Expectedness

The PI will be responsible for determining whether an AE is expected or unexpected. An AE will be considered unexpected if the nature, severity, or frequency of the event is not consistent with the risk information previously described for the study device.

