8.7 Safety Oversight

It is the responsibility of the Principal Investigator to oversee the safety of the study. This safety monitoring will include careful assessment and appropriate reporting of adverse events as noted above, as well as the construction and implementation of a site data and safety-monitoring plan. Medical monitoring will include a regular assessment of the number and type of serious adverse events. Data (demographics, eligibility criteria), screening methods, and adverse events will be assessed by the PI who is a fellowship trained interventional radiologist and licensed physician monthly to ensure study safety, compliance, and integrity/accuracy of data in accordance with the data safety monitoring plan.

Administration of study procedure will be halted when three moderate or higher grade AEs determined to be “related” are reported to the sponsor (PI). The PI will notify the study investigators immediately when the third grade 3 event is reported and enrollment screens will stop accepting new study participants. The study sponsor will convene a meeting with study investigators by teleconference or in writing as soon as possible and will provide recommendations for proceeding with the study. The study sponsor will inform the IRB and FDA of the temporary halt and the disposition of the study.

The outcomes of these reviews, when adverse events are captured will be communicated directly with the IRB. A summary of these reviews will be submitted to the IRB as part of an annual progress report at Continuing Review.

Specific data safety monitoring plan is listed below:

- 1- Vascular injury / non-target embolization to lower extremity, bleeding, access site complications will be monitored as follows:
 - a. On the day of procedure, interventional radiologist (investigator) performing the procedure will assess access site and lower extremity pulses and document
 - b. Day 1 visit / telemedicine visit: investigator will assess for symptoms in the target lower extremity (pain, swelling at access site and document findings
 - c. 4 weeks follow up visit: investigator will assess groin access site for hematoma, pseudoaneurysm and assess lower extremity pulses
- Skin ulceration, cutaneous purpura, plantar or peripheral sensory paresthesia will be monitored as follows:
 - Each follow up visit, an investigator will assess for symptoms and signs in the target lower extremity and document

CONFIDENTIAL

9 Clinical Monitoring/Quality Assurance

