Clinical site monitoring is conducted to ensure that the rights and well-being of human subjects are protected, that the reported trial data are accurate, complete, and verifiable, and that the conduct of the trial is in compliance with the currently approved protocol/amendment(s), with GCP, and with applicable regulatory requirement(s).

- Monitoring for this study will be performed by the study PI once every 3 months.
- Monitoring activities include communication with the sub-investigators and study site staff; review of the study site's processes, procedures, and records; and verification of the accuracy of data.

10 Statistical Considerations

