10.1 Statistical and Analytical Plans (SAP)

A formal SAP will not be performed prior to database lock since this study is a pilot study with no randomization.

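### The PI operates, sponsors, collects, monitors and analyses; the operator may judge which adverse events count toward the halt, and the responder cutoff for 40 patients is not fixed

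*Combined protocol and SAP*

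**What the plan says.** **Roles.** Section 1 makes the PI an operator and gives the same person the data and the analysis. The entry reads: "Will be one of two interventional radiologists performing the procedure. Will be responsible for study integrity, data monitoring, data collection, statistical analysis, and manuscript writing". Section 8.5 identifies the study sponsor as the PI, and 8.7 makes the PI responsible for overseeing safety, with a monthly review. Section 9 states: "Monitoring for this study will be performed by the study PI once every 3 months". That monitoring includes checking that the data are accurate. The Steering Committee in 16.1 is the PI and one co-investigator.

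**Halting count.** Section 8.7 states: "Administration of study procedure will be halted when three moderate or higher grade AEs determined to be" related, with reports going to the sponsor, who is the PI. On causality, 8.2.2 says that "the clinician who examines and evaluates the participant will determine" it. Severity is graded by the investigator (8.2.1). Neither section excludes the person who did the embolization.

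**Analysis.** Section 10.1 reads: "A formal SAP will not be performed prior to database lock since this study is a pilot study with no randomization". The rest of section 10 gives hypotheses, a rule of at least 16 responders among 23, an exact confidence interval method, a completers analysis set, and secondary and safety analyses. Section 10.5 raises the target to 40 evaluable patients (50 enrolled).

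**The concern.** In a single-arm, open-label trial with a patient-reported outcome, no comparator and no blinding is available to expose drift in either the response rate or the procedure-related adverse event rate. The protection has to come from separating the people who make the judgements and from fixing the analysis before the data are seen. Here both are thin.

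The halting rule is only as good as the relatedness calls that feed it, and a member of the operating team may make those calls about their own procedure. The person responsible for collecting the data also verifies them. The person who analyses the data is an operator with open access, and the written plan still leaves the pass mark and the exact definition of a responder to be settled. At stake are the credibility of the halt as a safeguard and of the claim that the response rate exceeds 50%.

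**Working it through.** **1. The plan's own figures.** Inputs from 10.2 and 10.5: null proportion 0.5, alternative 0.75, n = 23, cutoff 16. For a binomial count X, the tail is P(X ≥ c) = Σ C(n,x) pˣ(1−p)ⁿ⁻ˣ, summed from x = c to n.

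- Alpha = P(X ≥ 16 | 23, 0.5) = 0.0466. The plan says 0.047.
- Power = P(X ≥ 16 | 23, 0.75) = 0.8037. The plan says 80.4%.
- Attrition: 23/0.8 = 28.75, so 29; 40/0.8 = 50. Both agree with the plan.

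The analysis for 23 patients is therefore sound as written.

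**2. The same test at the current target.** No cutoff is given for 40. With the same formula and n = 40:

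| Cutoff | Alpha (p = 0.5) | Power (p = 0.75) |
|---|---|---|
| 25 | 0.077 | 0.974 |
| 26 | 0.040 | 0.946 |
| 27 | 0.019 | 0.897 |
| 28 | 0.008 | 0.821 |

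Twenty-six is the smallest cutoff that holds 5%. Twenty-eight comes from carrying over the proportion: 16/23 × 40 = 27.8. Reading 16 literally at n = 40 would give alpha 0.92. All can be argued from the present text.

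**3. Responder definition, side by side.**

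| Section | At least 50% fall in WOMAC pain | No increase in pain medication or injection |
|---|---|---|
| 3.1 | yes | yes |
| 10.4.1 | yes | yes |
| 4.1 | yes | not stated |
| 10.2 | yes | not stated |
| 10.4.2 | yes | not stated |

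A patient whose pain halves but who takes more analgesics is a responder under three sections and a non-responder under two.

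**4. The wording that feeds the halt.**

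- Section 8.7 gives two triggers: three related events of moderate or higher grade, and then the third grade 3 event. The severity scale in 8.2.1 is named, not numbered.
- Section 8.2.1 asks for relationship as yes or no. Section 8.2.2 uses three categories: not caused, unknown, caused. Section 8.7 counts related events without saying where unknown falls.
- Only the not-caused category requires a documented alternative cause, so calling an event unknown needs no such support.

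**5. How much the relatedness call can matter (illustration only).** None of these inputs is in the documents. Assume 50 treated patients, independent events, a true rate q of events that should count, and a fraction f of them called related. The chance of reaching a count of three is P(X ≥ 3 | 50, q·f):

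| q | f = 1 | f = 0.5 |
|---|---|---|
| 5% | 0.46 | 0.13 |
| 10% | 0.89 | 0.46 |
| 15% | 0.99 | 0.73 |
| 20% | 0.999 | 0.89 |

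The effect is large when events are uncommon and smaller when they are frequent. Conditioning on a fixed number of events shows the same pattern: with a 0.6 chance that each is called related, the count reaches three 48% of the time with four events, 68% with five, 82% with six and 95% with eight.

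**The case against.** The strongest reply is that this is a small single-site pilot under an IDE whose expansion the FDA approved (2.2), that the PI is not the only check, and that much of the complaint is preference. Several stronger readings are tempting, and the documents do not support them.

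- *No analysis is pre-set.* A reader might infer this from 10.1. It waives only a formal SAP; section 10 pre-sets an analysis whose figures reproduce. The defect is that it is incomplete for 40 patients and inconsistent on the responder.
- *The operator is assigned the causality call.* Section 8.7 has the operator check the access site and pulses on the procedure day and record the findings. It does not assign causality. The PI is also one of two operators, so judging one's own complications would arise in only part of the cases.
- *Expectedness feeds the halt.* Section 8.2.3 does say "The PI will be responsible for determining whether an AE is expected or unexpected", but the count in 8.7 turns on severity and relatedness.
- *Operators administer the pain forms.* No section says so. Patients mark their own pain scores, and the coordinator or an investigator transfers the data (4.1).
- *Nothing would reveal a bias.* Adverse events are recorded regardless of relationship (8.3), serious ones are reported regardless of relationship (8.5), and source records are open to audit (section 11).
- *The PI alone controls the halt.* The text says the procedure will be halted at the count, the investigators are convened, and the IRB and FDA are told.

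What stands of the reply is that these safeguards limit the harm. They do not close the gap. Notice to the IRB and FDA follows the internal count and does not test the calls behind it, and an audit trail helps only if someone uses it. Pilot status does not explain why a cutoff for the current sample size should be left open.

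**Conclusion.** The point holds as a cheap and worthwhile improvement. The concentration of roles is stated in the text, not inferred from silence: the PI is operator, sponsor, data collector, monitor, safety overseer and analyst. The operator is permitted to call relatedness for events that may count toward the halt, and the PI verifies data the PI is responsible for collecting.

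The firmest size is on the analysis side. At 40 evaluable patients, cutoffs from 25 to 28 move one-sided alpha from 0.077 to 0.008, and the responder definition differs between sections. This assumes that exactly 40 are evaluable. The halting figures show sensitivity under assumed rates and are not an estimate for this trial. Nothing in the documents shows that any call or analysis has in fact been biased.

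One limit: the list of roles in section 1 that was available for review is not complete, so other delegates may exist. The assignments to the PI are explicit and stand regardless.

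**What to change.** 1. **Sections 8.2.2 and 8.7.** Have a physician already on the protocol, who did not perform that patient's procedure, make the relatedness call for any event that could count toward the halt. The operator only describes the event. The Co-PI who does the knee OA clinical assessment is one candidate. That person also recruits, so this reduces the conflict and does not remove it. Reconcile the two trigger wordings in 8.7, and the yes/no scale in 8.2.1 with the three categories in 8.2.2, including how an unknown call is counted. Which trigger applies is for the sponsor to settle.
2. **Section 9.** Have source-data verification done by an existing team member who neither performed the procedure nor entered that patient's data.
3. **Section 10.1.** Replace the waiver with a short analysis specification, dated and signed before any efficacy summary is run and before lock. It should fix one responder definition and the cutoff for the current sample size, best stated as the smallest count with one-sided alpha of at most 5% at the number analysed: 26 at 40 (alpha 0.040), 32 at 50 (alpha 0.032). The PI may still run the analysis, but with these choices already closed.

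The cost is protocol wording, a delegation-log change and a few pages of specification, plus some scheduling load on the Co-PI and coordinator. On the roles visible in the protocol, no new staff should be needed.

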2.1 Background Information and Relevant Literature

Knee OA is common and major cause of pain and disability. Its prevalence is rising due to an aging population and the high prevalence of obesity [1]. Radiographically confirmed symptomatic knee OA affects approximately 3.8% of people worldwide, and knee and hip OA ranked as the 11th highest contributor to global disability [2]. Disabling symptoms of knee osteoarthritis are seen in an approximately 10 % of people over 55 years old [3]. Therefore, the prevalence and burden of knee OA presents a major challenge for health systems globally [2].

Knee OA is a complex, multifactorial disease with no known cure. Risk factors for knee OA include joint injury, bone and joint shape, muscle strength and mass, obesity, gender, metabolic factors, nutrition and vitamin factors, bone density, psychological health and occupation [4, 5]. Treatment seeks to manage symptoms, but adequate symptom control can be difficult to achieve [4-6]. Evidence-based treatment options for knee OA include intra-articular corticosteroids, exercise, education, weight management, and oral medications such as acetaminophen and non-steroidal anti-inflammatories for minor symptoms [7]. Total knee arthroplasty is generally reserved for those with severe joint disease, pain and functional limitations [8, 9]. On the other hand, moderate knee OA resistant to nonsurgical options, yet not severe enough to warrant joint replacement, does not have an optimal therapy. Therefore, there is still a need to develop an effective, minimally invasive and safe treatment for moderate OA of the knee.

An in-depth understanding of OA pathophysiology is still emerging [1]. Recently, angiogenesis has been implicated in OA by contributing to structural damage, inflammation and pain [10]. Angiogenesis is blood vessel overgrowth from pre-existing vasculature and is essential for growth, development and tissue repair [10]. However, in OA, angiogenesis increases in articular cartilage, synovium, meniscus, and osteophytes, and at the osteochondral junction [11-15]. Because angiogenesis is accompanied by sensory nerve growth, perivascular nerve growth into normally aneural structures such as articular cartilage and meniscus is thought to contribute to OA pain through chemical and mechanical stimulation of newly formed nerves. Modifying angiogenesis and associated nerve growth is a potential treatment pathway to affect the pathogenesis and symptoms of OA [10]. Angiogenesis inhibitor treatment decreased pain-related behavior in animal models [11]. The mechanism of symptomatic relief is unclear but could include reduced synovitis, reduced periarticular innervation and nociception, and maintaining the integrity of the osteochondral junction [10, 11].

A recent study by Padia S et al evaluated the safety and effectiveness of GAE in patients with knee OS (grades 2, 3, 4). Knee OA severity was grade 2 in 18% of the patients, grade 3 in 43%, and grade 4 in 40%. Technical success was achieved in 100% of the subjects. The WOMAC total and VAS pain scores decreased by 61% and 67% at 12 months from a median baseline of 52 (of 96) and 8 (of 10), respectively. Twenty-seven patients (68%) had a reduction of $\geq 50\%$ in both WOMAC total and VAS pain scores [32]. The WOMAC questionnaire is a widely used, disease-specific measure for knee OA. It includes 24 questions on daily activities: five regarding pain, two regarding stiffness, and 17 regarding physical function; possible score ranges for each subset of items are as follows: pain, 0–20; stiffness, 0–8; and physical function, 0–68. For each question in each of the three categories (pain, stiffness, and physical function) patients receive the following points: 0 for no symptoms, 1 for mild, 2 for moderate, 3 for severe, and 4 for extreme symptoms. Higher scores on the WOMAC indicate worse pain, stiffness, and functional limitation [16].

The Whole-Organ Magnetic Resonance Imaging Score (WORMS) in patients with knee OA provides multi-feature, whole-organ assessment of the knee in OA using conventional magnetic resonance imaging (MRI), and shows high inter-observer agreement among trained readers [17]. Whole-organ assessment could help discriminate different patterns of intra-articular involvement in OA; detect early, potentially preclinical, stages of OA;

CONFIDENTIAL

identify structural risk factors for developing clinical OA; or increase scope and sensitivity to change for monitoring disease progression and treatment response in patients with established OA. It takes into account a variety of features that are currently believed to be relevant to the functional integrity of the knee and/or potentially involved in the pathophysiology of OA. It scores each of these features with a sufficient number of increments to allow detection of what are speculated to be clinically relevant changes.

